- e. CMP-001 dosing will begin on W1D1. Weekly dosing: A window of ±2 days is permitted for CMP-001 dosing from W2D1 to W7D1. The first dose of CMP-001 may be administered SC or IT, at the discretion of the Investigator; all subsequent doses are planned to be administered IT until no injectable lesions remain. Subjects must complete all 7 weekly CMP-001 doses before moving to the Q3W dosing schedule. Q3W dosing (W10D1+): A window of ±3 days is permitted for CMP-001 dosing from W10D1 throughout the trial. When nivolumab is permanently discontinued due to an immune related AE, CMP-001 must also be permanently discontinued. Refer to Section 5.3 for Treatment Compliance.
- f. Nivolumab dosing will begin on W1D1 and continue Q3W throughout the study for a maximum of 2 years. For subjects in Arm A, when CMP-001 injection and nivolumab dosing fall on the same day, CMP-001 injection will be given before nivolumab dosing. Refer to Section 5.1.1 for Nivolumab Dosing.
- g. A full physical examination (PE) will be conducted at Screening and EOT. If the Screening full PE is performed >72 hours before the W1D1 visit, then a brief (symptom directed) PE must be performed within 72 hours before the first injection of CMP-001. Brief PEs focused on areas of disease or AEs must be performed at the W1D1, W3D1, W7D1 CMP-001 injection visits, at every CMP-001 injection visit thereafter, and at any other time as clinically indicated. Height will be obtained at Screening only and weight will be obtained at all PE assessments.
- h. Vital signs include measurement of blood pressure (systolic and diastolic blood pressure), respiratory rate, heart rate, and body temperature. Blood pressure and heart rate should be taken in the seated position following ≥3 minutes of rest. For subjects in Arm A, for the first 6 CMP-001 dosing visits (W1D1 to W6D1), vital signs must be collected prior to the CMP-001 injection and at 30-minute (±15 minutes) intervals for 4 hours after CMP-001 injection. Starting at W7D1, observation periods may be reduced to a minimum of 1 hour following CMP-001 injection at the Investigator's discretion based on the AE profile of the individual subject. When vital signs are scheduled at the same time as collection of a blood sample, the vital sign measurements should be obtained before the scheduled phlebotomy. If a study visit occurs where only nivolumab is administered, vital signs must be collected before the start of the nivolumab infusion.

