## 7.1.9. Vital Signs

Vital signs will be conducted as specified in the Schedule of Assessments (Table 1). Vital signs include measurement of blood pressure (systolic and diastolic blood pressure), respiratory rate, heart rate, and body temperature. Blood pressure and heart rate should be taken in the seated position following ≥3 minutes of rest. When vital signs are scheduled at the same time as collection of a blood sample, the vital sign measurements should be obtained before the scheduled phlebotomy. If a study visit occurs where only nivolumab is administered, vital signs must be collected before the start of the nivolumab infusion. If an indwelling cannula is being used to obtain blood, blood pressure should be measured in the arm opposite to the cannula placement.

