Baseline is defined as the last non-missing observation on or prior to the first administration of study drugs (CMP-001 or Nivolumab), including assessments on Day 1 that are pre-dose. Study Day 1 will be designated as the first day when a subject receives either study drug (i.e., Week 1 Day 1).

Regeneron Pharmaceuticals Inc. / Protocol: CMP-001-011 IQVIA Biotech (Confidential) Project # SZA58924

C. Missing Data

Unless stated otherwise, missing data will not be replaced with imputed values. When relevant, sections below will address how missing data will be handled for the particular analyses.

Missing or Partial Death Dates

A death date missing the month and day will be imputed as Jan 1st of the year or the day after the date of last known alive, whichever comes later.

A death date missing the day will be imputed as the 1st of the month or the day after the date of last contact, whichever comes later.

Missing Dates in Adverse Events/ Concomitant Medications

Every effort will be made to avoid missing/partial dates in on-study data including AE and medication start and stop dates.

Start dates of AEs/ Concomitant medications will be imputed as follows:

• Completely missing start date will not be imputed.

Start date missing both the month and day will be imputed as:

- The date of the first dose if the year of the start date is the same as the date of first dose.
- Otherwise, Jan 1st of the year of the start date will be used.

Start date missing the day will be imputed as:

- The date of first dose if the year and month of the start date are the same as the date of first dose.
- Otherwise, the 1st day of the month of the start date will be used.

Stop dates of AEs/ Concomitant Medications will be imputed as follows:

- Completely missing stop date will not be imputed.
- Stop date missing both the month and day will be imputed as Dec 31st of the year of stop date.
- Stop date missing the day will be imputed as the last date of the month of the stop date.

After imputation, the imputed date will be compared against the date of death, if available. If the planned imputed date is later than the date of death, the date of death will be used as the imputed date instead.

Regeneron Pharmaceuticals Inc. / Protocol: CMP-001-011 IQVIA Biotech (Confidential) Project # SZA58924

Missing Dates in Prior Medications

Start or Stop dates of Prior Medications will be imputed as follows:

- Completely missing start or stop date will not be imputed.

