Abbreviations: RBC = red blood cell; T3 = triiodothyronine; T4 = thyroxine; TSH = thyroid stimulating hormone; WBC = white blood cell.

Note: Refer to the Laboratory Manual for additional information.

E. Vital Signs

The following vital signs were measured at screening and periodic time points (including end of treatment) following the initiation of study treatment:

- Systolic and diastolic blood pressures (mmHg)
- Respiratory Rate (breaths/min)
- Pulse Rate (beats/min)
- Body temperature (Celsius)

Each of these vital signs will be summarized in a descriptive manner for the following values that will be derived per unique subject:

Regeneron Pharmaceuticals Inc. / Protocol: CMP-001-011 IQVIA Biotech (Confidential) Project # SZA58924

- Baseline value
- Minimum post-baseline value and corresponding change from baseline
- Maximum post-baseline value and corresponding change from baseline
- Last post-baseline value and corresponding change from baseline

The baseline value will be determined using the convention described in Section VI.B. Vital signs will be summarized by treatment arm and overall using descriptive statistics and presented for each time point from baseline to all subsequent post-baseline assessments, including the actual values and change from baseline, for the Safety Analysis Set. Clinically significant post-baseline vital sign findings will be reported as AEs. A by-subject data listing of all vital sign data will be generated.

F. Physical Examination

Detailed information on the physical examinations (height, weight, and BMI) will be listed by subject. Clinically significant post-baseline physical examination findings will be reported as AEs.

G. Prior and Concomitant Medications

All medications administered to the subject from 30 days prior to the first dose of the study drug (W1D1) until 100 days after the last dose of the study treatment (CMP-001 and nivolumab) or until the initiation of an alternative new anti-cancer treatment, whichever occurs first, will be recorded in the EDC. Treatment medications for AEs related to study treatment that occur more than 100 days after the last dose date of the study treatment will also be collected. In addition, at each LTSFU contact, an inquiry will be made regarding the start of any new cancer treatments since the date of the last contact.

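### By-arm vital-sign minima and maxima use all post-baseline readings, although only Arm A has scheduled post-injection series, so its extremes are expected to be wider even with no drug effect

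*SAP*

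**What the plan says.** **SAP IX.E (Vital Signs)** lists four derived values per subject: baseline, "Minimum post-baseline value and corresponding change from baseline", "Maximum post-baseline value and corresponding change from baseline", and the last post-baseline value. It does not limit the extremes to pre-dose readings or to time points common to both arms. It also states: "Vital signs will be summarized by treatment arm and overall using descriptive statistics and presented for each time point from baseline". The same section plans a by-subject listing and has clinically significant findings reported as AEs.

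**Protocol Table 1, footnote h** makes the schedule depend on arm. For Arm A at W1D1 to W6D1, "vital signs must be collected prior to the CMP-001 injection and at 30-minute (±15 minutes) intervals for 4 hours after CMP-001 injection". Later the series may be shorter: "Starting at W7D1, observation periods may be reduced to a minimum of 1 hour following CMP-001 injection at the Investigator's discretion".

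**Protocol 7.1.9** and footnote h cover the other case: "If a study visit occurs where only nivolumab is administered, vital signs must be collected before the start of the nivolumab infusion". No post-infusion series is specified there. In Arm B every dosing visit is of this kind.

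**SAP VI.B** sets baseline as the last non-missing value up to the first dose. The W1D1 post-injection readings therefore count as post-baseline and enter the extremes.

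**The concern.** The minimum of many readings is expected to be lower than the minimum of a few, and the maximum higher, even when both come from the same distribution. Arm A has many more scheduled readings per subject, so the extreme-value rows are not like for like.

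The extra Arm A readings also fall in a particular window. Protocol 5.1.3.2 names fever, hypotension and tachycardia among the CMP-001 symptoms, and expects symptoms mainly 1 to 4 hours after injection. Arm A is measured every 30 minutes in that window, and Arm B has no scheduled post-dose reading at all. A reader of the table could take lower minimum pressures, or higher maximum pulse and temperature, in Arm A as a measure of what CMP-001 adds. Part of that difference would come from the schedule.

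SAP IX.I says how replicate ECGs at one time point are handled (they are averaged). SAP IX.E has no such rule for vital signs, where repeated readings within a visit are built into the design for one arm.

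**Working it through.** The documents give no figure for this point, so there is none to reproduce.

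**Step 1: count scheduled post-baseline readings through W7D1** (Protocol Table 1 and footnote h).

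- Post-injection readings per visit in Arm A: 240 min / 30 min = 8. Over six visits: 6 × 8 = 48.
- Arm A total: 48 + 5 (pre-dose, W2D1 to W6D1) + 1 (W6D2) + 1 (W7D1 pre-dose) = 55. Any W7D1 post-injection readings would add to this.
- Arm B: 5 + 1 + 1 = 7 if it attends every vital-sign visit in Table 1, or 2 (W4D1, W7D1) if it attends nivolumab visits only. Table 1 is not split by arm, so both cases are carried.

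**Step 2: model with no drug effect.** Reading k at visit j is √ρ·b_j + √(1−ρ)·e_jk, with b and e independent standard normal. The total within-subject SD is 1 and the within-visit correlation is ρ. The documents give neither the SD nor ρ, so ρ is varied from 0 to 0.9. The expected per-subject minimum was simulated with 100,000 subjects per arm. Change from baseline has the same expected gap, because randomisation gives both arms the same expected baseline.

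**Step 3: results through W7D1, in SD units.**

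| ρ | Arm A (55) | Arm B (7) | Gap vs 7 | Arm B (2) | Gap vs 2 |
|---|---|---|---|---|---|
| 0 | −2.29 | −1.35 | 0.93 | −0.57 | 1.72 |
| 0.5 | −2.12 | −1.35 | 0.77 | −0.57 | 1.55 |
| 0.9 | −1.76 | −1.35 | 0.41 | −0.56 | 1.20 |

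The maximum is the mirror image. The chance of at least one reading below −2 SD is 32% to 72% in Arm A, against 15% (7 readings) or 4.5% (2 readings) in Arm B.

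**Step 4: extend to the period that the SAP uses.** SAP IX.E takes extremes over all post-baseline values, and vital signs continue at Q3W visits in both arms. With 7 Arm B readings to W7D1 and one reading per Q3W visit in each arm afterwards:

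- about 1 year (15 Q3W visits): gap 0.47 SD (ρ = 0), 0.36 (0.5), 0.16 (0.9);
- about 2 years (30 Q3W visits): gap about 0.3 SD (ρ = 0) down to 0.1 (0.9).

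If Arm A has two further post-injection readings at each Q3W visit (a 1-hour observation with 30-minute readings, which is an assumption), the 1-year gap is 0.60, 0.52 and 0.29 SD.

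**Step 5: scale, on an assumption only.** Suppose a within-subject systolic SD of 8 to 12 mmHg, which is not in the documents. Against 7 Arm B readings:

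- through W7D1: 0.41 × 8 = 3 to 0.93 × 12 = 11 mmHg;
- at 1 year: 0.16 × 8 = 1 to 0.47 × 12 = 6 mmHg;
- at 2 years: 0.1 × 8 = 1 to 0.3 × 12 = 4 mmHg.

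**Step 6: after matching.** With 7 single readings per arm, the mean minimum is −1.36 SD in both arms, the gap is 0.00 SD, and the chance of a reading below −2 SD is 15% in both.

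**The case against.** Much can be said for the plan as it stands.

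- **Other displays exist.** SAP IX.E also presents vital signs by time point, lists every value, and sends clinically significant findings to AE reporting. This is true, and those displays are much less affected. They do not correct the minimum and maximum rows, which stay in the same by-arm summary without a caveat.
- **The table is descriptive.** No test of vital signs is planned. SAP VI calls the analyses descriptive and exploratory, and SAP II.C reports 9 and 11 subjects. The listed safety endpoint in SAP IV.B is AEs and their severity. All of this stands and limits the weight of the point.
- **The gap shrinks with follow-up.** This stands: figures that stop at W7D1 overstate it for subjects treated for 1 or 2 years.
- **The counts are scheduled, not observed.** Protocol 7.4 says that some assessments may not be captured in the eCRF, and nothing confirms that each 30-minute reading is. The bias applies only to readings that are.
- **The bias would tend to overstate CMP-001 harm, not hide it.** This is a good reason to keep the all-readings extremes in the table.

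Two stronger readings are tempting. A reader might infer that the arms' extremes differ by measurement count alone. The documents do not support that, because a true acute effect is expected in the very window measured only in Arm A. A reader might also infer that the table is bound to show lower pressures and higher pulse and temperature in Arm A. With 9 and 11 subjects, the standard error of the arm difference in minimum change from baseline is about 0.5 SD in the same model, larger than the gap at 1 year with one reading per Q3W visit. Arm A also receives fluids and antipyretics around each injection (Protocol 5.1.2.1), which could push pressure and temperature the other way and are not in the model.

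**Conclusion.** The minimum and maximum rows in SAP IX.E are not comparable between arms as written. With no drug effect, Arm A's extremes are expected to be wider by about 0.4 to 0.9 SD through W7D1, 0.2 to 0.5 SD at 1 year and 0.1 to 0.3 SD at 2 years. These figures assume within-visit correlation from 0 to 0.9, 7 Arm B readings to W7D1, one reading per Q3W visit afterwards, and 30-minute readings that are in the database. If Arm B has only 2 readings to W7D1, the early gap is 1.2 to 1.7 SD.

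The observed difference will mix this artefact with any true CMP-001 effect, and the rows cannot separate them. Any mmHg figure depends on an SD that the documents do not give, so a single pressure gap should not be quoted as established. The point concerns the reading of a descriptive safety table and does not bear on the listed safety endpoint. It is worth correcting because the correction is cheap.

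**What to change.** In SAP IX.E:

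1. Add by-arm minimum and maximum rows derived only from pre-dose readings, plus readings at non-dosing visits such as EOT, at visits attended in both arms. Use these rows for the between-arm display. The SAP must name those visits, since Protocol Table 1 does not say which ones Arm B attends.
2. Keep the all-readings minimum and maximum, with a footnote that Arm A has scheduled post-injection readings and Arm B has no scheduled post-dose readings.
3. Add an Arm A-only table of post-injection readings: the largest rise and the largest fall from the same-day pre-injection value, by dose number.
4. Leave the last post-baseline value as it is. It carries no extreme-value bias, and a pre-dose-only rule would drop EOT.

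The cost is SAP wording, one extra set of rows and one extra table, all from data already collected. No assessment or clinical procedure changes.
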